9.2 TREATMENT COMPLIANCE

Study medication dosing compliance for a specified period is defined as the total dose (mg actually taken by a patient during that period divided by the prescribed dose expected to be taken during the same period multiplied by 100. An overall per-dose compliance measure can be calculated by (# of actual dose administrations)/ (Total # of expected dose administrations) *100 during the subject's treatment period. Descriptive statistics for study medication compliance will be presented by treatment group for the entire treatment period of the study.

Compliance will be summarized as follows:

- Descriptive statistics will be summarized by the 2 treatment groups for entire treatment period.
- Percent compliance will be categorized according to the following categories for entire treatment period for safety population by the 2 treatment groups:
 - less than 50% (significant drug noncompliance)
 - at least 50%, less than 75% (moderate drug noncompliance)
 - greater or equal 75% (drug compliance)
 - unknown

10 PRIOR AND CONCOMITANT MEDICATIONS

The World Health Organization Drug Dictionary (WHO Drug) will be used to classify prior and concomitant medications by therapeutic class and generic name based on ATC code level 3. Prior medication is defined as any medication taken and stopped prior to the first dose of the study medication. Concomitant medication is defined as any medication taken between the day of first dose of the study medication and the day of last study medication date + 28 days.

Medication start and end dates and times will be compared with the start date of study drug and classified as per Table 3.

In case of partial or missing dates, comparisons will be made based on the level of detail available. For example, if start date of study drug is 04Jan2013, and a medication has a start date of Jan2013 but missing day, the medication will be classified as concomitant.

Table 3: Classification of prior and concomitant medications

Start date \ End date	Before start of study drug administration	On or after start of study drug administration	Missing
Before start of study drug administration	Prior	Concomitant	Concomitant
On or after start of study drug administration	–	Treatment Emergent Concomitant	Treatment Emergent Concomitant
Missing	Prior	Concomitant	Concomitant

Both prior and concomitant medication usage will be summarized by the number and proportion of subjects in each treatment group. Subjects will only be counted one time in each unique ATC Class and generic name if multiple drugs are used by a subject.

Detailed analyses may be performed on prior and concomitant medications of special interests such as oral iron, blood pressure medications and lipids medications.

11 EFFICACY ANALYSES

Efficacy analysis will be conducted on the ITT and FAS for US (FDA) submission and analysis for non-inferiority on the PPS population and analysis for superiority on FAS population for EU regulatory submission.

The **Efficacy Emergent Period** is defined as the evaluation period from the Analysis date of first dose intake up to 7 days after the Last Dose of study drug or EOT Visit, whichever occurs first. This period will be used as reference period for the time to event analyses related to efficacy endpoints, unless specified otherwise.

11.1 ANALYSIS OF PRIMARY ENDPOINT

11.1.1 Primary Endpoint

There are 2 primary efficacy endpoints: one for the US submission and one for the Ex-US submission.

The primary efficacy endpoint for the US submission is the Mean Hb change from baseline (using central laboratory values) to the average level during the Evaluation Period, defined as Week 28 until Week 52. This analysis will be based on the intent-to-treat (ITT) population. Hemoglobin values under the influence of rescue therapy will not be censored for the primary analysis.

The primary efficacy endpoint for the Ex-US submission is defined as the proportion of subjects who achieve a Hb response at two consecutive visits during the first 24 weeks of treatment, without rescue therapy within 6 weeks prior to the Hb response. This analysis will be based on the PPS population.

- A Hb response is defined, using central laboratory values, as: Hb ≥ 11.0 g/dL and a Hb increase from baseline by ≥ 1.0 g/dL in subjects whose baseline Hb > 8.0 g/dL, or
- Increase in Hb ≥ 2.0 g/dL in subjects whose baseline Hb ≤ 8.0 g/dL.

Rescue therapy for roxadustat treated subjects is defined as ESA rescue or RBC transfusion, and rescue therapy for Epoetin alfa treated subjects is defined as RBC transfusion.

11.1.2 Primary Analysis

Efficacy analysis for superiority will be conducted on the ITT population for US (FDA) submission and on the FAS population for Ex-US submission.

Efficacy analysis for non-inferiority will be conducted on the ITT population for US (FDA) submission and on the PPS population for Ex-US submission.

US (FDA) Submission: The primary efficacy endpoint for US (FDA) submission is defined as the mean Hb change from baseline to the average level during the Evaluation Period, defined as Week 28 until Week 52. The analysis will be based on the ITT

population. Hb values under the influence of rescue therapy will not be censored for the primary efficacy analysis.

The primary hypothesis to be tested for the primary efficacy analysis is:

H_0 : Hb mean change from baseline to the average level from Week 28 to Week 52 in the roxadustat arm \leq Hb mean change from baseline in the epoetin alfa arm minus 0.75 g/dL

Versus:

H_1 : Hb mean change from baseline to the average level of Week 28 to Week 52 in the roxadustat arm $>$ Hb mean change from baseline in the epoetin alfa arm minus 0.75 g/dL

A multiple imputation analysis of covariance (MI ANCOVA) model will be used. The model will contain terms for treatment group, baseline Hb measurement, and stratification factors except Screening Hb values (≤ 8 g/dL vs. > 8 g/dL). The primary efficacy analysis will be based on the estimated difference between the two treatments overall mean effects throughout the evaluation period based on the pooled ANCOVA model.

This null hypothesis will be rejected if the two-sided 95% CI for the difference between the two treatment groups using MI ANCOVA model lies entirely above -0.75 g/dL.

The following steps will be used to conduct the primary analysis of the primary endpoint:

1. Generate 200 datasets, using seed 162345 for the U.S., where only intermittent missing hemoglobin data will be imputed for each treatment relying on non-missing data from all subjects within each treatment group using the Monte Carlo Markov Chain (MCMC) imputation model baseline hemoglobin, and the available non missing hemoglobin for each scheduled Week by treatment group.

The MCMC statement in the SAS PROC MI procedure with monotone option will be used. As a result, each dataset will only have missing ending data, or a monotone missing data pattern.

2. For each dataset from step 1, missing ending data (hemoglobin up through end of evaluation period) will be imputed. As a result, 200 imputed complete datasets will be generated.

- Missing data at Week 1 will be imputed using the regression imputation model with baseline stratification factor, baseline and hemoglobin from Week 1, using the SAS PROC MI procedure with the REGRESSION option in the MONOTONE statement.
- The SAS PROC MI procedure will use data separately from each treatment subjects to impute the missing data for a specific Week (i.e. only those that need the imputation for the Week). Since subjects from the different treatment groups for that Week are excluded from the step, they will not contribute to the imputation for the Week.
- Repeat for all other scheduled Weeks sequentially (Week 2 to the end of evaluation period). Subjects whose missing data were imputed for previous Weeks will contribute to the imputation for the current Week.

- The regression imputation model includes an intercept and the slopes of the hemoglobin from previous Weeks.

3. Analyze each imputed complete dataset using the ANCOVA model using the mean of all observed or imputed Hb values within the evaluation period (Week 28 – 52). The model will contain terms for baseline Hb measurement as a covariate, treatment group and stratification factors except Screening Hb values (≤ 8 g/dL vs. > 8 g/dL) as fixed effects.

Sample SAS code:

```
PROC MIXED data=xx;
  class treatment categorical covariates;
  model change_Week36 = treatment covariates / solution;
  lsmeans treatment / diff cl;
  ods output Diffs=lsdiffs LSMeans=lsm solutionF=Parms;
  by _Imputation_;
run;
```

4. Combine estimates from the results for each of the 200 ANCOVA model using SAS PROC MIANALYZE.

```
PROC MIANALYZE parms(classvar=full)=lsdiffs;
  class treatment categorical covariates;
  modeleffects treatment;
  ods output ParameterEstimates=MIAN_lsdiffs;
run;
```

Report the results of the least-squares mean estimates of the change from baseline in hemoglobin during the evaluation period, the estimates of treatment effect (e.g. least-squares mean CFB in hemoglobin for the treatment group minus the least-squares mean CFB in hemoglobin for the active comparator group) and the corresponding p-values during the evaluation period.

The analysis will be repeated with Hb values under the influence of rescue therapy censored. Namely, set Hb to missing for Rescue Medication and 6 weeks afterwards (or 8 weeks if during the evaluation period).

Ex-US Submission: The primary efficacy endpoint for Ex-US submission is defined as the proportion of subjects who achieve an Hb response at two consecutive visits during the first 24 weeks of treatment, without rescue therapy within 6 weeks prior to the Hb response.

- A Hb response is defined, using central laboratory values, as: $Hb \geq 11.0$ g/dL and a Hb increase from baseline by ≥ 1.0 g/dL in subjects whose baseline $Hb > 8.0$ g/dL, or
- Increase in $Hb \geq 2.0$ g/dL in subjects whose baseline $Hb \leq 8.0$ g/dL

Rescue therapy for roxadustat treated subjects is defined as ESA rescue or RBC transfusion, and rescue therapy for epoetin alfa treated subjects is defined as RBC transfusion.

The hypothesis to be tested for the primary efficacy analysis is:

H_0 : Hb response rate for subjects in the roxadustat arm - Hb response rate for subjects in the epoetin alfa arm $\leq -15\%$

Versus

H_1 : Hb response rate for subjects in the roxadustat arm - Hb response rate for subjects in the epoetin alfa arm $> -15\%$

A two-sided 95% CI for the difference of 2 responder rates (roxadustat minus epoetin alfa) based on the Miettinen & Nurminen approach adjusting for treatment and stratification factors will be calculated and this null hypothesis will be rejected if the lower bound of the 95% CI is greater than -15%. Subjects who dropped out from the study without data for the assessment will be treated as non-responder.

11.1.3 Sensitivity Analyses of Primary Endpoint

The following secondary analyses will be performed on the U.S. primary efficacy endpoint as sensitivity analyses to examine the potential impact of missing data on the estimates. These analyses will be performed using ITT Population. The results of the analyses will be summarized in Table 4. These sensitivity analyses are further detailed in each Section.

Table 4: U.S. Primary Endpoint Analysis Results

Analysis (ITT Population)	Trt Diff and 95% CI (roxadustat vs EPO)	Std. Err.	Degree of Freedom*	t-statistics	p-value
ANCOVA with Multiple Imputations (Primary)	.xx (.xx, .xx)	.xx	XXX	.XXX	.XXXX
ANCOVA-MI with Hb censored**for rescue therapy	.xx (.xx, .xx)	.xx	XXX	.XXX	.XXXX
MMRM	.xx (.xx, .xx)	.xx	XXX	.XXX	.XXXX
PMM-Last Mean Carried Forward	.xx (.xx, .xx)	.xx	XXX	.XXX	.XXXX
PMM –Baseline Carried Forward (Roxadustat only)	.xx (.xx, .xx)	.xx	XXX	.XXX	.XXXX
PMM –Baseline Carried Forward (Both Groups)	.xx (.xx, .xx)	.xx	XXX	.XXX	.XXXX

$$df = (m-1) \left(1 + \frac{m \bar{U}}{(m+1)B} \right)^2. \quad \text{where B is}$$

* Maximum of Degree of Freedom from each individual ANCOVA. The actual Degrees of Freedom in PMM will be calculated using

$$\bar{U} = \frac{1}{m} \sum_{j=1}^m U_j.$$

between-imputation variance and with U the standard error associated with estimates, Rubin (1987).

** Set Hb to missing for Rescue Medication and 6 weeks afterwards (or 8 weeks if during the evaluation period)

11.1.3.1 MMRM Model

A mixed model of repeated measures (MMRM) will be used as one sensitivity analysis for the primary endpoint for US Submission (change from baseline in Hb from Week 28 to Week 52).

The model will contain terms for treatment arm, baseline measurement, visit (up to Week 52), visit by treatment interaction, and stratification factors except Screening Hb values (≤ 8 g/dL vs. > 8 g/dL). The primary efficacy analysis (for US [FDA]) will be based on the estimated difference between the two treatments overall mean effects throughout the evaluation period based on the MMRM model. Hb values under the influence of a rescue therapy will not be censored in the primary analysis.

Due to the large amount of visits to include in the model, data up to Week 52, the unstructured covariance pattern model will be applied first. If the algorithm for unstructured covariance pattern does not converge or the likelihood ratio test is not statistically significant then heterogeneous Toeplitz structure will be used. If this second model does not converge either then the (homogeneous) Toeplitz structure will be tried and finally compound symmetry as a covariance structure to achieve convergence. If none of them converge, first order autoregressive (AR (1)) as a covariance structure will be used to achieve convergence.

11.1.3.2 Pattern Mixture Model (PMM)

PMMs provide a general and flexible framework for sensitivity analyses that allows formulating assumptions regarding missing data in a transparent and clinically interpretable manner. This is expected to address the possibility of the data being missing not at random (MNAR). All factors mentioned in the primary analysis will be included in the PMM.

The following aspects of missing data, may affect the estimates.

- Timing and extent of missing data
- Assumed underlying mechanism for missing data

11.1.3.2.1 Timing and Extent of Missing Data

To assess the potential effect of missing data on the estimate of treatment effect, subjects will be classified as full data or missing data cases. Patterns of missing data will be based on non-missing hemoglobin before the end of the evaluation period.

- Full data cases are defined as subjects without any missing hemoglobin values for all scheduled assessments in the evaluation period.
- Missing data cases are defined as subjects with a missing hemoglobin on at least one scheduled Visit Week of the evaluation period. The missing data cases are further grouped into intermittent missing and monotone missing cases.

- Intermittent missing hemoglobin cases are defined as subjects with a missing hemoglobin for at least one scheduled week of but not on consecutive scheduled weeks up to end of the evaluation period.
- Monotone missing hemoglobin cases are defined as subjects who have consecutive scheduled Weeks with missing hemoglobin up to the end of evaluation period. A subject who is a Monotone missing case could have intermittent missing hemoglobin prior to the ending Week.

Subjects will be grouped as follows:

- Full data cases
- Intermittent missing data cases
- Monotone missing data cases

Should the incidence of Monotone missing data cases and intermittent missing data cases be relatively small, then those cases will be combined so that the groups are full data cases and missing data cases. The summary of missing pattern in first 52-week scheduled visit will be presented by treatment group in a table.

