
Description of Change	Rationale for Change	Section(s) Affected a

Treatment Period (added text is italicized, revised text is bolded and italicized):
 
Treatment duration is variable for individual subjects. In order to complete the Treatment Period simultaneously for all study subjects, the minimum treatment duration may be less than 52 weeks, with a maximum treatment duration of up to approximately 3 years after the last subject is randomized. Subjects will be informed at least 4 weeks prior to their treatment period end.
	
In order to complete the Phase 3 program in a timely manner and simultaneously for all study subjects, the minimum treatment duration of subjects enrolled after March 2017 (as part of Amendment 4) may be less than 52 weeks. Such subjects will be informed at least 4 weeks in advance if such a decision is made.
	Synopsis , Section 3.1

Procedures for Handling Incorrectly Enrolled Subjects
 
The following section was added:
 
Subjects who fail to meet all eligibility criteria should not be enrolled. If it is discovered in retrospect that a subject did not meet all eligibility criteria, the Investigator should inform the Medical Monitor immediately, and a discussion should occur regarding whether or not to discontinue the study subject. All decisions from such a discussion should be appropriately documented.
	
This language was added to align the protocol with a new SOP for protocol templates
	Section 3.3

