## 3 STUDY DESIGN

### 3.1 Description of the Study

This is a Phase 3, multicenter, randomized, open-label, and active-controlled study to evaluate the efficacy and safety of roxadustat in the treatment of anemia in incident-dialysis subjects.

The study periods are as follows:

- **Screening Period:** Up to 6 weeks
- **Treatment Period:** Treatment duration is variable for individual subjects. In order to complete the Treatment Period simultaneously for all study subjects, the minimum treatment duration may be less than 52 weeks, with a maximum treatment duration of up to approximately 3 years after the last subject is randomized. Subjects will be informed at least 4 weeks prior to their treatment period end.
- **Post-Treatment Follow-Up Period:** 4 weeks

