## 6.1.2 Treatment Period

Eligible subjects will be randomized via IXRS to receive roxadustat or epoetin alfa. The Treatment Period begins on the first day of dosing with study treatment (Day 1/Week 0). A common closeout will occur when a predetermined number of adjudicated CV, cerebrovascular or thromboembolic events have been accrued across the entire Phase 3 program.

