3 STUDY DESIGN

This is a Phase 3, multicenter, randomized, open-label, and active-controlled study to evaluate the efficacy and safety of roxadustat in incident dialysis subjects with anemia.

A total of up to 1,200 subjects are planned to be randomized to receive roxadustat or epoetin alfa (active control) in a 1:1 ratio, respectively.

Randomization stratification factors include geographical region (US vs. Ex-US), screening Hb values (≤ 8 g/dL vs. >8 g/dL), and cardiovascular/cerebrovascular/thromboembolic medical history (yes vs. no).

In addition, the change of protocol were incorporated via amendments on 20 Oct 2014, 24 Nov 2015, 12 Aug 2016, and current one on 20 September 2017.

Subjects randomized to roxadustat will have doses administered thrice weekly (TIW) throughout the Treatment Period using an initial tiered, weight-based, dosing scheme (see Table 1 below), followed by dose titration every 4 weeks.

Table 1. Initial Study Drug Dosing

Study Drug (Dose Frequency)	Low Weight/Dose	Median Weight/Dose	High Weight/Dose
Roxadustat (TIW) – Original Protocol	45 to 60 kg/70 mg	>60 to 90 kg/100 mg	>90 to 160 kg/150 mg
Roxadustat (TIW) – Amended Protocol	≤ 70 kg/70 mg		>70 to 160 kg/100 mg
Epoetin alfa HD (TIW)	IV dosing according to epoetin alfa USPI or SmPC		
Epoetin alfa PD (TIW)	Epoetin alfa should be administered according to epoetin alfa USPI or SmPC or local standard care.		
	Abbreviations: HD = hemodialysis; IV = intravenous; PD = peritoneal dialysis; SmPC = summary of product characteristics; TIW = three times a week; USPI = United States Package Insert; wt = weight. Note: Weight in HD subjects = subject's dry weight.		

The study periods are as follows:

- Screening Period: Up to 6 weeks
- Treatment Period: Treatment duration is variable for individual subjects with maximum treatment duration of up to approximately 3 years after the last subject is randomized. The minimum treatment duration may be less than 52 weeks.
- Post-Treatment Follow-Up Period: 4 weeks

Dose Adjustments

Roxadustat arm

Dose adjustments will occur in two separate study dosing phases: the Correction Phase and the Maintenance Phase. Each of these phases will follow unique dose adjustment rules according to Appendix 2 in the amended protocol of 20 October 2014. All subjects in the roxadustat arm will be dosed orally TIW during the Treatment Period. The maximum roxadustat dose is 3.0 mg/kg per dose or 400 mg, whichever is lower.

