11.1.3.2.4 PMM –Baseline Carried Forward (Roxadustat Only and Both Groups)

The analysis is the same as PMM – Last Mean Carried Forward except imputing the missing data. The imputation data will be generated similarly as last mean carried forward method described above but instead of using post-baseline observed data, only baseline data will be used. The similar analyses will be conduct in two scenarios.

- The baseline carried forward imputation will be performed for the roxadustat treatment group only, while for active control group, the imputation data will be generated using the last mean carried forward described above.
- The baseline carried forward imputation will be performed for the both treatment groups.

Similarly, the Rubin’s method will be then used to combine the estimates and the differences between the least square mean differences between the two treatment groups from each of the ANCOVA analysis. This sensitivity analysis will be performed for U.S. primary endpoints only.

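### The SAP's pattern-mixture analyses do not separate sponsor close-out before Week 52 from dropout, so both Baseline Carried Forward rows of Table 4 carry a bias set by the calendar

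*SAP*

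**What the plan says.** **Treatment can end early for administrative reasons.** Protocol 3.1 states that "the minimum treatment duration may be less than 52 weeks", and SAP section 3 repeats this; neither gives a lower floor. Protocol 6.1.2 ties the end of treatment to the programme, not to the subject: "A common closeout will occur when a predetermined number of adjudicated CV, cerebrovascular or thromboembolic events have been accrued". The Amendment 4 rationale says who is exposed: "the minimum treatment duration of subjects enrolled after March 2017 (as part of Amendment 4) may be less than 52 weeks".

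**Missing-data patterns ignore the reason for stopping.** SAP 11.1.3.2.1 has three groups: full data, intermittent missing and monotone missing. The last is defined by missing values only: "Monotone missing hemoglobin cases are defined as subjects who have consecutive scheduled Weeks with missing hemoglobin up to the end of evaluation period".

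**The imputed value depends on the analysis.**
- Primary MI ANCOVA (SAP 11.1.2): missing values are imputed within arm from that arm's own data.
- MMRM (11.1.3.1): missing values are left missing.
- Last Mean Carried Forward (11.1.3.2.3): the arm's own mean at the last observed visit is used.
- Baseline Carried Forward (11.1.3.2.4): baseline data only. In one scenario "The baseline carried forward imputation will be performed for the roxadustat treatment group only", with last mean for epoetin alfa; in the other, baseline is used in both arms.

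No section makes an exception for close-out.

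**The concern.** SAP 11.1.3.2 offers the pattern-mixture models as a check against data missing not at random, and 11.1.3.2.2 recognises that the mechanism behind the missing data matters. Close-out is a known mechanism, triggered by an event count across the programme and not by the subject's Hb. A late enrollee who is responding well and is stopped by the sponsor is nevertheless handled like one who stopped for lack of effect. In the Baseline Carried Forward runs, that subject's remaining Week 28–52 values are drawn as if the Hb rise had vanished.

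What is at stake is how two rows of SAP Table 4 can be read. A poor roxadustat-only result could reflect the close-out date rather than the drug. A reassuring both-arm result could come partly from giving both arms the same untreated level.

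**Working it through.** **Inputs**
- Margin −0.75 g/dL, SD 1.25 g/dL, at least 600 subjects (SAP 5.1); 1:1 allocation, so 300 per arm. Variant: about 1000 subjects (SAP 5.1), so 500 per arm.
- True difference d: −0.30 in SAP 5.1, +0.30 in protocol 8.1. The signs disagree, so both are used, together with 0.
- Mean Hb rise D: about 2 g/dL after 6 weeks in the Phase 2 incident-dialysis study (protocol 1.4.2.2). No Week 28–52 value is given; assumed range 1 to 3.
- f, the share of roxadustat subjects closed out early: not given.
- w, the share of the seven scheduled Week 28–52 visits that such a subject misses: 7/7 = 1.0 if the last visit is Week 24, 4/7 = 0.57 if Week 36, 1/7 = 0.14 if Week 48.

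**The plan's own figure.** SE = 1.25 × √(2/300) = 0.102. The distance from −0.30 to −0.75 is 0.45. Power = Φ(0.45/0.102 − 1.96) = 99.3%, which agrees with the stated 99% or more.

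**Roxadustat-only run.** If stopping is unrelated to Hb, the expected estimate is d − f·w·D, and the chance that the 95% CI lies above −0.75 is Φ((d − f·w·D + 0.75)/SE − 1.96). With d = −0.30, D = 2 and 300 per arm:

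| f·w | Expected estimate (g/dL) | Chance CI lies above −0.75 |
|---|---|---|
| 0 | −0.30 | 99% |
| 5% | −0.40 | 93% |
| 10% | −0.50 | 69% |
| 15% | −0.60 | 31% |
| 20% | −0.70 | 7% |

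The expected lower limit equals −0.75, so that the chance is about 50%, when f·w = (d + 0.75 − 1.96·SE)/D. Here 1.96·SE is 0.200 at 300 per arm and 0.155 at 500 per arm.

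| d | 300 per arm | 500 per arm |
|---|---|---|
| −0.30 | (0.45 − 0.200)/2 = 12.5% | (0.45 − 0.155)/2 = 14.8% |
| 0 | (0.75 − 0.200)/2 = 27.5% | (0.75 − 0.155)/2 = 29.8% |
| +0.30 | (1.05 − 0.200)/2 = 42.5% | (1.05 − 0.155)/2 = 44.8% |

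At d = −0.30 and 300 per arm, a rise of 3 gives 0.25/3 = 8.3% and a rise of 1 gives 0.25/1 = 25%. The point estimate itself reaches −0.75 at 0.45/2 = 22.5%.

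In subjects rather than values: if last visits are spread evenly over Weeks 24 to 48, the mean w is 4/7 = 0.57, so f·w = 12.5% means about 0.125/0.571 = 22% of roxadustat subjects closed out early.

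**Both-arm run.** With the same share lost in each arm, the estimate is (1 − f·w)·d. At f·w = 20%, −0.30 becomes −0.24, so this run does not fail because of close-out. The error runs the other way: a true difference of −0.75 would become −0.60, and the chance of clearing the margin would rise from 2.5% to about 31% (SD held at 1.25).

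**Simulation check** (simplified multiple imputation; 300 per arm, d = −0.30, variance parameters taken as known). Cells show mean estimate and share of runs with the CI above −0.75.

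| Analysis | 15% cut at Week 24 | 30% cut evenly over Weeks 24–48 |
|---|---|---|
| Roxadustat-only baseline | −0.61; 23% | −0.65; 12% |
| Both-arm baseline | −0.27; 97% | −0.25; 99% |
| Last mean | −0.31; 98% | −0.31; 100% |
| Within-arm missing at random | −0.31; 98% | −0.30; 100% |

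The roxadustat-only passing rate at 15% is below the formula's 31%, partly because mixing treated and baseline levels widens the spread.

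**The case against.** **A one-arm baseline imputation is meant to be harsh.** It is a deliberate worst case, shown beside gentler analyses, and readers will discount it accordingly. This stands as a reason not to drop the run. It does not justify applying the penalty to subjects whose reason for stopping is known and administrative.

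**The size is uncertain.** The 2 g/dL rise comes from 6 weeks in a 60-subject study, d differs in sign between the two documents, and nothing shows how many subjects would be closed out, or that any would stop before Week 28. All of this stands, which is why thresholds are given and not a prediction.

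**Close-out may not be wholly unrelated to outcome.** Those exposed are late enrollees, recruited under the wider Amendment 4 eligibility criteria. This stands in part. The protocol-version factor in SAP 5.4 covers some of it, and a return to untreated baseline would be a poor model for such differences in any case.

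**Some reporting already exists.** SAP 11.1.3.2.1 plans a missing-pattern table by arm, and SAP section 6 a listing of premature discontinuations by reason. These would help a reader but leave the imputation unchanged.

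**Conclusion.** The point holds for the two Baseline Carried Forward rows. In the roxadustat-only row, close-out biases the difference against roxadustat by about D times the share of roxadustat Week 28–52 values lost. Whether that matters depends on assumptions: losses of 12.5% to 14.8% bring the expected lower limit to −0.75 under the SAP's −0.30 and a 2 g/dL rise, while under the protocol's +0.30 it takes 42.5% to 44.8%. True dropouts use up part of the same allowance. In the both-arm row the bias is towards no difference.

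A reader might infer more than the documents support:
- *That all pattern-mixture runs set these subjects to baseline.* Last Mean Carried Forward does not, and in the roxadustat-only scenario neither does the epoetin alfa arm.
- *That a key sensitivity analysis would fail, or that the US primary result is at risk.* The SAP ranks no sensitivity analysis as key and attaches no pass rule to these rows. The −0.75 rule belongs to the MI ANCOVA, which imputes within arm.
- *That crossing the threshold means certain failure.* It marks about an even chance.
- *That the ex-US responder analysis has the same fault.* SAP 11.1.2 says: "Subjects who dropped out from the study without data for the assessment will be treated as non-responder". A subject stopped by the sponsor is not plainly a dropout, and one who has already responded has data. That is a missing detail, not a demonstrated bias.

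**What to change.** In SAP 11.1.3.2.1, add a separate pattern for subjects whose treatment the sponsor ended at common close-out before Week 52. In every pattern-mixture run, impute their missing values from the primary within-arm missing-at-random model. Apply baseline or last-mean carried forward only to subjects who stopped before close-out. Report the numbers closed out before Week 28 and before Week 52, by arm, beside Table 4.

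This keeps the stress test for true dropouts and leaves the expected difference unchanged by close-out if stopping is unrelated to Hb within arm.

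The cost is SAP wording and one flag. The discontinuation reasons in protocol 6.1.3.2 include no close-out category, so the flag may have to be derived from planned End of Treatment (6.1.2.5) versus Early Termination (6.1.2.6), checked against the close-out date. Late enrollees may still differ from earlier ones, and the protocol-version factor handles that only in part.
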